6.3. End of treatment / withdrawal

If a patient experiences an event that meets the criteria in "4.3.1 Discontinuation Criteria", the patient's treatment will be terminated. At the end of the study treatment or withdrawal from the study, if the patient has not been examined within 14 days prior to the end of the study, the following tests should be conducted:

[Hematology] [Blood Chemistry] [Urinalysis] [Stool Routine] [Coagulation Function]
[Pregnancy Test] [Thyroid Function Test] [Myocardial Zymogram] [Vital Signs]

[Physical Examination] [ECOG Score] [Electrocardiogram] [Blood Pressure Monitoring] [Adverse Events] [Concomitant Medications] [Recovery of Apatinib]

If no imaging examination has been performed within 4 weeks prior to the end of treatment, an imaging examination should be conducted at the end of the study treatment or upon withdrawal from the study for efficacy evaluation. For patients with non-imaging evidence of progression (intolerable, other circumstances), tumor assessments should be performed every 3 months until disease progression, death, or initiation of other anti-tumor treatments.

6.4. Follow-up

Thirty (30) days after the termination/completion of treatment (30 days \pm 3 days after the last administration of the investigational drug)

[Vital Signs] [Physical Examination] [ECOG Score] [Hematology] [Urinalysis] [Blood Chemistry] [Adverse Events] [Concomitant Medications]

SAEs and irAEs will be followed up within 90 days after the last administration of SHR-1210. If the patient initiates a new anti-tumor treatment, follow-up should be performed until the initiation of the anti-tumor treatment if it starts within 30 days after the last administration, follow-up should be performed until at least 30 days after the last administration; if it starts after 30 days, follow-up should be performed until the initiation of the anti-tumor treatment).

[Survival Follow-up] After the termination of the study treatment, the survival status and subsequent anti-tumor treatment information can be collected every month through clinical follow-up or telephone follow-up until death.

7. Evaluation

7.1. Efficacy evaluation

7.1.1. Efficacy endpoints

The primary efficacy endpoint of this study is the ORR assessed based on RECIST 1.1 criteria.

ORR: It refers to the proportion of subjects who complete at least one efficacy evaluation after treatment and have a best overall response (BOR) of CR or PR according to RECIST 1.1 criteria. If first CR or PR is achieved, the response should be confirmed no less than 4 weeks \pm 7 days after the first evaluation.

BOR refers to the best response recorded during the period from the date of initiation of treatment to the date of recorded objective progression according to RECIST 1.1 criteria or the date of initiation of new anti-tumor treatment (whichever occurs first).

For subjects who have not shown documented progression and have not initiated new anti-tumor therapy, the BOR will be determined based on all efficacy assessment results.

For subjects who continue to receive SHR-1210 after progression, the BOR should be determined based on the efficacy evaluation results recorded up to the initial occurrence of progression as defined by RECIST 1.1.

Secondary efficacy endpoints included:

- The ORR assessed by the investigator based on RECIST 1.1 criteria;
- PFS: It is defined as the time from the date of the first administration of the investigational drug to the date of the first documented tumor progression (assessed according to RECIST 1.1 criteria, regardless of whether the treatment is continued) or the date of death due to any cause (whichever occurs first).

In determining PFS, clinical deterioration occurring in the absence of definitive evidence of disease progression (according to RECIST 1.1) is not considered as disease progression. For subjects who have not previously reported progression before death, the death date will be considered as the date of disease progression. Subjects

with neither disease progression nor death will be censored on the date of their last evaluable tumor assessment. Subjects with no tumor assessments during the study and no death will be censored on the date of first treatment. Subjects who discontinue the study due to reasons other than disease progression (without subsequent radiological examination) will be censored at the time of study discontinuation. Subjects who have not previously reported disease progression but initiate subsequent anti-tumor therapy will be censored on the date of the last evaluable tumor assessment before starting subsequent anti-tumor therapy or at the time of initiating subsequent anti-tumor therapy. When subjects are not censored at the time of study discontinuation or the time of initiating subsequent anti-tumor therapy, the prescheduled sensitivity statistical analysis will only further confirm PFS based on the time of radiologically confirmed progression event. The occurrence of new tumors is not considered a disease progression event and is not used for data censoring.

- TTR: It is defined as the time from the date of first administration to the date of the first recorded tumor response (assessed according to RECIST 1.1 criteria).
- DoR: It is defined as the time from the date of first recorded tumor response (assessed according to RECIST 1.1 criteria) to the date of first recorded tumor objective progression (assessed according to RECIST 1.1 criteria) or the date of death due to any cause. Subjects with neither disease progression nor death will be censored on the date of their last tumor assessment. Subjects who start receiving any subsequent anti-tumor treatment (excluding treatment for non-target bone lesions or palliative radiotherapy during the study treatment) and have not previously reported progression will be censored at the time of their last tumor assessment prior to starting subsequent anti-tumor treatment, or on the day of starting subsequent anti-tumor therapy.

- 6-month survival rate: It is defined as the proportion of patients with a survival duration of ≥ 6 months from the date of initial treatment;
- 9-month survival rate: It is defined as the proportion of patients with a survival duration of ≥ 9 months from the date of initial treatment;
- 12-month survival rate: It is defined as the proportion of patients with a survival duration of ≥ 12 months from the date of initial treatment;
- OS: It is defined as the time from the date of first drug administration to the date of death due to any cause. For subjects who are still alive at the last follow-up, their OS data will be censored at the last follow-up. For subjects who are lost to follow-up, their OS data will be censored at the last confirmed survival time before being lost to follow-up. The censored OS is defined as the time from the date of first drug administration to the date of data censoring.

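### PFS has two overlapping censoring dates for subjects who leave without progression, and both PFS and DoR leave the censoring date at new therapy as an unresolved either/or

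*Protocol*

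**What the plan says.** All the rules are in Protocol section 7.1.1.

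**PFS.** Subjects "with neither disease progression nor death will be censored on the date of their last evaluable tumor assessment". Subjects with no tumor assessment on study and no death are censored at first treatment. The next sentence reads: "Subjects who discontinue the study due to reasons other than disease progression (without subsequent radiological examination) will be censored at the time of study discontinuation". Anyone without reported progression who starts new anti-tumor therapy is censored at the "last evaluable tumor assessment before starting subsequent anti-tumor therapy or at the time of initiating subsequent anti-tumor therapy". A sentence on sensitivity analysis follows: where subjects are not censored at discontinuation or at therapy start, "the prescheduled sensitivity statistical analysis will only further confirm PFS based on the time of radiologically confirmed progression event".

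**DoR.** The general rule is "Subjects with neither disease progression nor death will be censored on the date of their last tumor assessment". With new therapy, the date is that of the last tumor assessment "prior to starting subsequent anti-tumor treatment, or on the day of starting subsequent anti-tumor therapy". DoR has no study-discontinuation rule and no sensitivity sentence.

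Section 10.5.3 estimates both endpoints by Kaplan-Meier with 95% confidence intervals. Section 10.2 leaves detail to an SAP, but requires a revision of an endpoint definition or its analysis to appear in an amended protocol as well.

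**The concern.** A subject who leaves the study alive, without progression and without a later scan, meets two PFS rules with two different dates, and no precedence is stated. If the later date is used, the interval between last scan and departure counts as progression-free although nobody looked for progression. The either/or at new therapy has the same effect in PFS and DoR. Two analysts who follow the protocol faithfully could report different curves from the same data. In a single-arm study there is no control arm in which the same distortion would also appear, so reported PFS and DoR take it in full.

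**Working it through.** The protocol states no PFS assumption, dropout rate or expected median, so there is no figure to reproduce. The check has four steps.

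**1. The rules side by side (section 7.1.1).**

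| Subject without progression or death | PFS date | DoR date |
|---|---|---|
| General rule | last evaluable assessment | last assessment |
| No assessment on study | first treatment | not applicable |
| Left the study, no later imaging | study discontinuation | no separate rule |
| Started new therapy | last prior assessment, or therapy start | last prior assessment, or therapy start |

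For PFS, row 3 is a subset of row 1 with a later date. It also overlaps row 2, although a subject with no efficacy evaluation would fall outside the full analysis set of section 10.3. Row 4 is open for both endpoints. The second date in row 4 also departs from each endpoint's own general rule.

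**2. Direction.** The Kaplan-Meier estimate is S(t) = Π(1 − d_j/n_j), with d_j events and n_j at risk at each event time. A later censoring date leaves every d_j as it is and can only keep or increase n_j. Each factor, and so the whole curve, is therefore equal or higher.

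**3. How long the gap can be.** Inputs: a 4-week cycle (section 5.2), and scans every 2 cycles for 12 cycles, then every 3 (section 7.1.2), within ±7 days (section 6.2).
- First 12 cycles: 2 × 4 = 8 weeks, or 8 + 2 = 10 with windows.
- Later: 3 × 4 = 12 weeks, or 12 + 2 = 14 with windows.
- At end of treatment: at most about 4 weeks, if the scan required by sections 6.3 and 7.1.2 is done.
- No upper limit for a subject who refuses visits but stays in survival follow-up (section 4.3.2; monthly telephone contact in section 7.1.2) and later leaves alive.

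**4. Size, by simulation.** From the protocol: n = 30 and the scan schedule above. Assumed, because the protocol gives no values: exponential progression with true median 4, 6 or 9 months; 10, 20 or 30% leaving before progression; 0, 12 or 24 further weeks in the study without scans; administrative follow-up of 26 weeks plus uniform 0 to 130 weeks. Each scenario has 2,000 runs, and the same data are censored both ways. The table gives the mean rise in Kaplan-Meier median PFS, in months, with discontinuation instead of last-scan censoring. Ranges span the three true medians.

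| Leaving without progression | 0 extra weeks (mean gap about 4 weeks) | 12 extra weeks | 24 extra weeks |
|---|---|---|---|
| 10% | 0.08 | 0.29–0.35 | 0.52–0.61 |
| 20% | 0.16–0.19 | 0.71–0.77 | 1.19–1.36 |
| 30% | 0.28–0.35 | 1.32–1.35 | 2.30–2.35 |

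At 4.345 weeks per month, the first column is 0.08 × 4.345 = 0.3 weeks to 0.35 × 4.345 = 1.5 weeks. The 6-month PFS estimate rises by 0–2, 1–11 and 1–16 percentage points across the three columns.

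A second set of 4,000 runs per scenario (true median 26 weeks, scanning stops at a random time in the first 26 weeks) gives:
- 20% leaving 12–26 weeks after scanning stops: median 30.8 to 34.6 weeks, a rise of 3.8 weeks or 3.8/4.345 = 0.87 months; 26-week PFS 52.6% to 57.3%.
- 10% leaving 12–26 weeks after: 31.0 to 32.6 weeks.
- Leaving within 0–8 weeks: 30.7 to 31.6 weeks.

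The benchmark with no dropout is about 30.2 weeks and 52.7%, so last-scan censoring stays close to it. If deaths during the unscanned period count as PFS events (assumed median post-progression survival of 13–26 weeks), a shift of about 3.7 weeks falls to 2.7–2.9.

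The either/or at new therapy was not simulated. Its direction follows from step 2; its size depends on the interval from last scan to new therapy, for which the protocol gives no figure.

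**The case against.** The best defence is that the discontinuation sentence is a specific exception to the general rule. The sensitivity sentence can be read to support this: it implies a main analysis that censors at discontinuation or therapy start, and a planned sensitivity analysis that does not. On that reading PFS discontinuation is a debatable choice rather than a contradiction. This has some force, but the protocol never states the precedence, the sentence does not choose between the two new-therapy dates, and it does not cover DoR. Even as a deliberate exception, the rule credits unscanned time.

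The second defence is that stopping treatment is not leaving the study. Subjects who stop for toxicity or deterioration are due an end-of-treatment scan and then scans every 3 months (sections 6.3 and 7.1.2). Section 4.3.2 also asks for continued imaging, and a death without prior progression is a PFS event. This stands: a long gap needs a subject who stops scans against schedule, stays in contact and later leaves alive.

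A reader might infer three further things that the document does not support.
- **DoR is also censored at study discontinuation.** That rule appears under PFS only; the DoR defect is the either/or.
- **The date will be picked after the data are seen.** The SAP is not at hand and may fix it beforehand, although section 10.2 would then call for a matching protocol change.
- **PFS and DoR contradict each other on palliative radiotherapy.** DoR carves out some treatment ("excluding treatment for non-target bone lesions or palliative radiotherapy during the study treatment"), while PFS and best overall response are silent on it. Silence is not a contradiction, and it gives no ground to alter the response definition behind ORR.

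**Conclusion.** The point holds as a defect in the endpoint definitions. PFS has overlapping censoring rules without precedence, one of which counts unscanned time as progression-free. PFS and DoR each leave the date at new therapy undetermined.

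Compared with last-scan censoring, the later PFS date gives an equal or higher estimate. The shift in median is about 0.1 to 0.35 months, around a week, when subjects are scanned on schedule until they leave. It is roughly a month or more only with 20% or more of subjects stopping scans and leaving 12–26 weeks later. The figure of nearly 4 weeks belongs to that second situation and should not be read as the expected effect. All sizes rest on the assumed medians, dropout shares and unscanned intervals, and on departure being unrelated to impending progression. No size is claimed for DoR.

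Both endpoints are secondary and descriptive, with no test or threshold attached, and primary ORR is unaffected. The text should be corrected, but the study's main result does not depend on it.

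**What to change.** In section 7.1.1, give one date per situation in the main definitions:

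- **PFS:** without progression or death, censor at the last evaluable tumor assessment and, if new anti-tumor therapy has started, at the last evaluable one before it. With no post-baseline assessment and no death, censor at first dose.
- **DoR:** without progression or death, censor at the last tumor assessment, and at the last one before any new anti-tumor therapy.
- Delete the study-discontinuation date from the main PFS definition, and the therapy-start alternative from both PFS and DoR.
- Reword the sensitivity sentence so that discontinuation (PFS) and therapy start (PFS and, if wanted, DoR) are named there as the alternative dates. A sensitivity analysis is already foreseen for PFS; as written, it seems to place the later dates in the main analysis.

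The cost is protocol wording, with the SAP aligned under section 10.2. No visits, scans or subjects are added. The downside is that PFS and DoR come out equal or slightly less favourable. Last-scan censoring also does not remove bias if subjects leave because they are about to progress; the scans already required at end of treatment and every 3 months are the protection against that.

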4.3.2. Procedures for withdrawal from the study or termination of study treatment

It is essential to diligently complete the efficacy and safety assessments specified in

the protocol when withdrawing from the study, as well as to complete the safety follow-up period, and comprehensively record AEs and their outcomes.

The investigator may suggest or provide new or alternative treatment methods to the study subjects based on their actual conditions.

Patients without disease progression should continue to be followed up for radiological evaluation until the subject starts a new anti-tumor treatment or disease progression. If a subject refuses to come to the study site for further visits, his/her survival status should still be followed up, unless the subject withdraws consent for further disclosure of information or further contact. In such cases, no further study evaluations should be conducted, and no additional data should be collected. The sponsor may retain and continue to use all data collected before the subject withdraws his/her informed consent, unless the subject requests the withdrawal of the already collected information.

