7.1.2. Efficacy evaluation criteria

The primary and secondary efficacy endpoints of SHR-1210 in combination with apatinib mesylate in the treatment of advanced mucosal malignant melanoma will be evaluated according to RECIST v1.1.

The lesions identified at baseline should be examined every 2 cycles during the first 12 treatment cycles (bone scans should be performed when there is suspicion of bone progression or when confirming a CR), and every 3 cycles thereafter. This schedule is not affected by interruptions or delays in treatment. If new lesions are suspected, timely examinations can be performed. The first PR or CR must be confirmed 4 weeks \pm 7 days later. If disease progression is observed according to RECIST 1.1, imaging examinations should be performed 4 ~ 6 weeks later for confirmation (except for rapid progression and significant clinical progression).

Survival records and assessment: After the treatment withdrawal, the subjects will be

followed up once a month for survival status via telephone, until death, loss to follow-up, withdrawal of informed consent, or termination of the study. The evaluation of tumor response will involve all known or suspected sites of lesions.

Radiological imaging examinations include CT scans or MRI scans of the chest, abdomen, or pelvis; brain CT or MRI scan is used for subjects with known or suspected brain metastases; bone scan is used for subjects with known or suspected bone metastases (see section 7.1 for details on imaging examinations).

If the overall health condition of a subject deteriorates, requiring discontinuation of the medication, but there is no objective evidence of disease progression at this time, it should be reported as symptomatic worsening.

If no imaging examination has been performed within 4 weeks before the end of treatment, an imaging examination should be conducted at the end of the study treatment or upon withdrawal from the study for efficacy evaluation. For patients with non-imaging evidence of progression (intolerable, other circumstances), tumor assessments should be performed every 3 months until disease progression, death, or initiation of other anti-tumor treatments.

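### The PFS sensitivity analysis in 7.1.1 needs radiological progression from patients who have no planned or no later scan, so it barely tests informative censoring

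*Protocol*

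**What the plan says.** Protocol section 7.1.1 defines PFS from first dose to RECIST 1.1 progression or death, and states that clinical deterioration without RECIST evidence is not progression. Two of its censoring rules matter here.

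- Leaving the study: "Subjects who discontinue the study due to reasons other than disease progression (without subsequent radiological examination) will be censored at the time of study discontinuation".
- New therapy without earlier progression: "censored on the date of the last evaluable tumor assessment before starting subsequent anti-tumor therapy or at the time of initiating subsequent anti-tumor therapy".

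The sensitivity analysis comes next in the same paragraph. The situation it addresses is "When subjects are not censored at the time of study discontinuation or the time of initiating subsequent anti-tumor therapy". What it may use in that situation is then restricted: "the prescheduled sensitivity statistical analysis will only further confirm PFS based on the time of radiologically confirmed progression event".

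The imaging rules are elsewhere. Section 4.3.2: "Patients without disease progression should continue to be followed up for radiological evaluation until the subject starts a new anti-tumor treatment or disease progression". Section 6.3, for patients who come off treatment without imaging progression: "tumor assessments should be performed every 3 months until disease progression, death, or initiation of other anti-tumor treatments". Section 7.1.2 repeats that rule. It also says of a patient whose general decline forces treatment to stop without objective progression that "it should be reported as symptomatic worsening". Section 6.4 provides for monthly collection of survival status and subsequent anti-tumor therapy until death.

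**The concern.** A sensitivity analysis that lifts a censoring rule is informative only if something can be observed after the censoring date. Here the two rules are lifted, but the one outcome admitted is progression on imaging. In both groups of patients, imaging is what is missing after that date.

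Patients who switch therapy or leave before documented progression may be closer to progression than those who stay. If so, censoring them is informative and raises the PFS curve. The trial has one arm and about 30 patients, so no internal comparator absorbs such a bias. A sensitivity result close to the main one could then be read as evidence of robustness when the analysis had almost no means of differing.

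**Working it through.** **Step 1: the rules side by side**

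| Rule lifted | Patients affected | Planned tumor assessments after the censoring date | Progression events gained |
|---|---|---|---|
| Censoring at new therapy | Those who switch before documented progression | None: 4.3.2, 6.3 and 7.1.2 all end assessment when new therapy starts | None from planned assessments |
| Censoring at study discontinuation | Only those without a later scan | None, because the group is defined that way | None |

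The reasons differ. For new therapy, the protocol stops the scans. For discontinuation, it does not stop them: the rule simply selects patients who had none. This table carries the conclusion.

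**Step 2: how large the untested bias could be (illustration)**

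The protocol states no PFS figure and no switch rate, so there is nothing of its own to reproduce. Only n = 30 (section 10.1) comes from the document. The other inputs are assumptions:

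- exponential PFS with true median 6 months, so true 6-month PFS = exp(−ln 2 × 6/6) = 0.50;
- a further exponential time to death with median 8 months;
- follow-up uniform on 6 to 36 months;
- a share of 10, 20 or 30% who switch at 80% of their own time to progression, with no scan afterwards;
- switchers censored at the last scan before the switch, with scans every 1.84 months (8 weeks, that is two 4-week cycles);
- 1,500 simulated trials per share.

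Kaplan-Meier: S(6) = product over event times u ≤ 6 of (1 − d_u/n_u). Mean results are events, then 6-month PFS:

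| Analysis | 10% switch | 20% switch | 30% switch |
|---|---|---|---|
| Main rule | 23.2; 0.526 | 20.5; 0.563 | 18.1; 0.593 |
| Rules lifted, imaging only | 23.2; 0.526 | 20.5; 0.563 | 18.1; 0.593 |
| Rules lifted, deaths also counted | 24.9; 0.530 | 24.0; 0.567 | 23.2; 0.595 |
| Switch counted as an event | 25.9; 0.489 | 26.0; 0.485 | 26.2; 0.474 |

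The first two rows are equal because no scan after a switch was assumed. They restate step 1 and do not add evidence for it.

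Main rule minus switch-as-event:

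- 10%: 0.526 − 0.489 = 0.037
- 20%: 0.563 − 0.485 = 0.078
- 30%: 0.593 − 0.474 = 0.119

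Against the true 0.50, the main rule is high by 2.6, 6.3 and 9.3 points. The switch-as-event estimate is low by 1.1, 1.5 and 2.6 points.

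A second simulation had n = 30 and scans every 8 weeks to week 48, then every 12. The same shares of failures were censored at the last scan, and PFS was read at 26 weeks. It gave 0.560 against 0.525, 0.590 against 0.520 and 0.630 against 0.520, which are gaps of 3.5, 7.0 and 11.0 points. With true medians of 4 and 8 months included, the gaps were about 3, 6 to 8, and 10 to 12 points.

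These gaps measure the main censoring convention. They show what a useful sensitivity analysis would have to reveal.

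**Step 3: would counting deaths rescue the stated analysis?**

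Deaths add 24.9 − 23.2 = 1.7, 24.0 − 20.5 = 3.5 and 23.2 − 18.1 = 5.1 events of 30. Yet 6-month PFS moves by at most 0.004 (0.526 to 0.530), and upward. Under these assumptions most such deaths come too late to show the bias at 6 months.

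**The case against.** Several points on the other side are sound.

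- **Scans do not stop when treatment ends.** A reader might infer that imaging ceases at both censoring points. Sections 3.1, 4.3.2, 6.3 and 7.1.2 say otherwise: patients who stop treatment without progression and do not switch stay on tumor follow-up, and their later progression or death counts in the main PFS. Section 6.3 also asks for a scan at end of treatment or withdrawal if none was done in the previous 4 weeks.
- **Some events could still appear.** A reader might infer that the analysis can add no event and must repeat the main result. That is too strong. Section 6.2 allows unscheduled imaging when progression is suspected, and the synopsis (Study Visits) has annual brain and bone imaging until the end of the study. It is also unclear whether the restriction to radiological progression excludes deaths. Dates could shift without new events, because the new-therapy rule allows two censoring dates. The phrase on confirmed progression could also refer to the 4 to 6 week confirmation scan.
- **The statistical analysis plan is not shown.** Section 10.2 leaves detailed methods to it, so one cannot say that this is the only PFS sensitivity analysis planned. It is the only one in the protocol text.
- **RECIST-based PFS is a deliberate choice.** Counting clinical worsening as an event departs from it.
- **PFS is secondary and descriptive.** ORR, the primary endpoint, is unaffected.

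These points limit the claim without removing it. Optional or annual scans are not a planned source of progression dates after a switch. Shifted dates do not tell us what happened to the switchers. A composite event belongs beside the main PFS and leaves its definition alone. And the concern is with an analysis that the protocol itself specifies, not with one that is absent.

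**Conclusion.** The point holds in a limited form. The sensitivity analysis in 7.1.1 lifts censoring at discontinuation and at new therapy but relies on radiological progression alone. Planned assessments end at new therapy, and the discontinuation group has no later scan by definition. The analysis can gain essentially no radiological progression event and is a very weak check on informative censoring of patients who switch or leave before documented progression.

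The size of any bias is hypothetical: roughly 3 to 12 points in 6-month PFS for assumed switch shares of 10 to 30%, with every switcher near progression. Switches for toxicity, which those simulations leave out, would make it smaller. The documents do not support calling the main PFS biased by any given amount. Severity is minor.

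**What to change.** In 7.1.1, replace or supplement the stated analysis with one that:

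1. counts the start of subsequent anti-tumor therapy without earlier documented progression as a PFS event on its start date;
2. as a further variant, also counts a treatment stop reported as symptomatic worsening under 7.1.2, on its date;
3. states that deaths after withdrawal count as events and, if the existing analysis is kept, that deaths after a switch count in it;
4. is reported beside the main RECIST-based PFS, which stays as it is.

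The same edit should choose one of the two censoring dates that the main new-therapy rule now allows.

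The cost is a sentence or so in 7.1.1 and one more Kaplan-Meier run, with a second run for the variant. The inputs are already provided for: subsequent therapy and survival status under 6.4, symptomatic worsening under 7.1.2. No imaging or care changes. The downside is that switches for toxicity count as events, so the estimate is conservative. That suits a bounding analysis if it is labelled as one.
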